5.3.3 Reasons for Withdrawal and Discontinuation of Study Product Administration

Subjects may voluntarily withdraw their consent for study participation at any time without penalty or loss of benefits to which they are otherwise entitled.

An investigator may also withdraw a subject from receiving the study product for any reason. Follow-up safety evaluations will be conducted, if the subject agrees. If a subject withdraws or is withdrawn prior to completion of the study, the reason for this decision must be recorded in the case report forms (CRFs).

The reasons, might include, but are not limited to the following:

- Subject no longer meets eligibility criteria
- Subject withdraws consent
- Subject not able to comply with study procedures
- Subject becomes noncompliant
- Evidence of toxicity including study drug-related AE/SAE, laboratory abnormality, intercurrent illness, or other medical condition or situation occurs that continued participation in the study would not be in the best interest of the subject.
- Medical disease or condition, or new clinical finding(s) for which continued participation, in the opinion of the investigator might compromise the safety of the subject, interfere with the subject's successful completion of this study, or interfere with the evaluation of responses
- Subject lost to follow-up
- Decision by the Investigator that termination is in the subject's best medical interest.
- Decision by the sponsor to stop or cancel the study
- Decision by local regulatory authorities (IRB/IEC) to stop or cancel the study
- Determined by a physician's discretion to require additional therapy not indicated in the protocol to ensure subject's health and well-being (or treatment failure, if applicable)

The investigator should be explicit regarding study follow-up (e.g. safety follow-up) that might be carried out despite the fact the subject will not receive further study product. If the subject consents, every attempt will be made to follow all AEs through resolution. The procedures that collect safety data for the purposes of research must be inclusive in the original informed consent or the investigator may seek subsequent informed consent using an IRB/IEC-approved consent form with the revised procedures.

The investigator will inform the subject that already collected data will be retained and analyzed even if the subject withdraws from this study.

5.3.4 Handling of Withdrawals

Subjects who withdraw or are withdrawn from participation in the study at any time. Subjects may also withdraw voluntarily from receiving the study intervention for any reason. An investigator may also withdraw a subject from receiving further intervention

Subjects who withdraw, or are withdrawn from the efficacy endpoint analysis, or are lost to follow-up after signing the informed consent form, randomization, and receipt of study product will not be replaced. Subjects who withdraw consent after signing the informed consent form and randomization but before receipt of study product may be replaced.

If a subject withdraws from the study after receiving any amount of study drug the subject will be asked to continue scheduled study procedures including safety and efficacy evaluations, if possible, and be given appropriate care under medical supervision if symptoms of any AE related to participation in the study are continuing. The participant will be followed until the AE is resolved or until the subject's condition becomes stable.

Subjects who request to withdraw their consent after study treatment from further participation in the study will be reminded of the importance of continuing the study for safety evaluations and will be encouraged to complete the Early Termination Visit if they choose not to complete the remaining study visits. The Early Termination Visit procedures are listed in Section 7.4. Subjects who choose to decline continuation in study participation will no longer be contacted for follow-up.

If a subject is withdrawn at any time due to an AE, the event will be followed until it is resolved or in the opinion of the Investigator is determined medically stable with the consent from the subject. The site PI may request unblinding of the study drug assignment if they feel that such information is essential for the management of an AE or SAE. If the PI feels that unblinding is essential for management of the AE or SAE, they will request unblinding by contacting the DMID Medical Monitor. Clinical failure is not an acceptable reason to request unblinding.

Refer to the MOP and the DMID policy "Unblinding Individual Participants in DMID Clinical Research," the current policy is available at <https://www.niaid.nih.gov/research/dmid-data-management>.

In the case of subjects who fail to appear for a follow-up safety assessment, extensive effort (i.e., three documented contact attempts via phone calls, e-mails, etc., made on separate occasions and followed by a certified letter) will be made to locate or recall them, or at least to determine their health status. Although the subject is not obliged to give reasons for withdrawing early, the

investigator should make a reasonable effort to ascertain the reasons while fully respecting the subject's rights. These efforts will be documented in the subject's records.

5.3.5 Termination of Study

The study will be terminated if the DSMB determines that the study should be terminated based on safety concerns. If the study is terminated, the DSMB will be permitted to allow the longitudinal monitoring phase of the study to proceed. DMID and/or the IND holder may terminate the study at their sole discretion. Although the sponsor had every intention of completing this trial, it reserves the right to terminate this trial at any time for clinical or administrative reasons. Reasons for termination include, but not limited to, study closure due to DSMB review and recommendation and at the discretion of DMID.

If the study is prematurely terminated by the sponsor, any regulatory authority, or the investigator for any reason, the investigator will promptly inform the study subjects and assure appropriate therapy or follow-up for the subjects, as necessary. The investigator will provide a detailed written explanation of the termination to the IRB/IEC.

5.3.6 Recruitment and Retention

Study subjects are seen either inpatient or clinic setting, and the Transplant Infectious Disease team is notified and consulted on all patients diagnosed with Norovirus. All candidates at all centers that are eligible to be included in the study will be offered the opportunity to participate in the trial.

The transplant patient population have a proven track record of a high compliance and retention rate in research related activities. The study subject clinical appointments will be adjusted to coincide with their research visit windows to ensure convenience. In addition, the subjects will be compensated for their research study visit.

6 STUDY INTERVENTION/INVESTIGATIONAL PRODUCT

6.1 Study Product Description

Nitazoxanide is a synthetic antiprotozoal agent for oral administration. It is designated chemically as 2-acetyloxy-N- (5-nitro-2-thiazolyl) benzamide. The molecular formula is $C_{12}H_9N_3O_5S$ and the molecular weight is 307.3. The placebo will look identical to nitazoxanide, and will have the same inactive ingredients (described in section 6.1.2).

6.1.1 Acquisition

Romark, L.C. will provide any necessary nitazoxanide 500mg tablets and matching placebo at no cost. Upon request from DMID, the study products (nitazoxanide and placebo) will be shipped to the following address:

DMID Clinical Materials Services (CMS)
Fisher BioServices
[name]
[name]
[contact]
[contact]
Email: [contact]

Study products, nitazoxanide 500mg tablets and matching placebo will be shipped from DMID CMS to investigational site upon request and approval by DMID.

6.1.2 Formulation, Packaging, and Labeling

Nitazoxanide Tablets

Nitazoxanide will be supplied as a 500 mg round, yellow, film-coated tablet with “CTM” imprint, manufactured by Romark, L.C. Per the package insert, inactive ingredients include: maize starch, pregelatinized corn starch, hydroxypropyl methylcellulose, sucrose, sodium starch glycollate, talc, magnesium stearate, soy lecithin, polyvinyl alcohol, xanthan gum, titanium dioxide, FD&C Yellow No. 10 Aluminum Lake, FD&C Yellow No. 6 Aluminum Lake, and FD&C Blue No. 2 Aluminum Lake.

Placebo Tablets

Placebo will be supplied as a matching tablet of the active drug which will also be a round, yellow, film-coated tablet with “CTM” imprint. Ingredients include: lactose monohydrate, magnesium stearate, talc, soy lecithin, polyvinyl alcohol, xanthan gum, titanium dioxide, FD&C

Yellow No. 10 Aluminum Lake, FD&C Yellow No. 6 Aluminum Lake, and FD&C Blue No. 2 Aluminum Lake. In order to maintain the blind, the placebo will be formulated for the same appearance as the active study drug.

Package and Labeling

All study product will be packaged in two 60cc identical containers each containing 30 tablets. Each container will also be labeled in compliance with applicable regulatory requirements, including the FDA-required cautionary statement “*Caution: - New drug -Limited by Federal Law to Investigational Use.*”

6.1.3 Product Storage and Stability

Nitazoxanide and Placebo for Nitazoxanide tablets must be stored at 25°C (77°F); excursions are permitted to 15-30°C (59-86°F). [See USP Controlled Room Temperature].

The temperature of the storage unit must be manually recorded daily (excluding non-business days and holidays, as applicable) and continuously monitored and recorded during the course of this trial per the participating site standard operating procedures (SOPs), and documentation will be maintained. If the temperature fluctuates outside of the required range, the affected study product(s) must be quarantined at the correct storage temperature and labeled as ‘Do Not Use’ (until further notice). The participating site’s research pharmacist must alert the site principal investigator and study coordinator, if the temperature fluctuates outside of the required range. In the event the temperature fluctuates outside of the required range, including accidental deep-freezing or disruption of the cold chain, the affected study product(s) must not be administered. The site principal investigator or responsible person should immediately contact the DMID Product Support Team at [contact] for further instructions before any additional study product are administered. Based on the information collected, DMID and/or the manufacturer will determine whether the affected study product(s) can be used. If it cannot be used, the site will receive specific instructions on how to return the affected study product(s) to the DMID CMS or destroy it on site.

For subjects in the hospital, the participating sites will maintain a temperature log to record temperature once per day in the room where the study products are stored for the period that the patient is in the hospital.

6.2 Dosage, Preparation and Administration of Study Intervention/Investigational Product

Nitazoxanide (administered orally as one 500 mg tablet) or placebo (administered orally as a matching tablet) twice daily with food for 56 doses. If the patient is NPO, product can be taken with water.

Subjects in the hospital will be provided the study drug consistent with the site SOP while ambulatory subjects will be provided two bottles, each containing 30 tablets.

A Site Research Pharmacist may be delegated the responsibility of study product dispensation. The Research Pharmacist must be a licensed, registered pharmacist and is the preferred healthcare practitioner to be delegated to perform this activity. If a Research Pharmacist is not available, a physician, nurse practitioner, physician assistant, registered nurse, or other authorized healthcare practitioner who is a member of the clinical study staff may be delegated to dispense the study product. These personnel must be licensed, trained, and qualified to prepare investigational study product and must be authorized to dispense the study product under state and local rules and regulations.

6.3 Modification of Study Intervention/Investigational Product for a Participant

There will be no modification of the dose of nitazoxanide during the 56 dose treatment phase. Subject's discontinuation of study treatment will be determined by the study site physician.

6.4 Accountability Procedures for the Study Intervention/Investigational Product(s)

Study product will be stored and shipped from the DMID contract repository, Fisher BioServices, to the Clinical Sites. Once received, study product will be stored in and dispensed by the Investigational Pharmacy.

Used/opened product will be counted and disposed in accordance with site's SOPs with two staff members (two research pharmacists or a research pharmacist and/or a study team member) present co-signing and verifying the count (see MOP for additional detail). In addition, this verification form will be added to the protocol file so that DMID monitors can verify when at the sites for a routine IMV. In addition, used/opened product can also be retained until monitored and released for disposition, as applicable.

The United States Food and Drug Administration (FDA) requires accounting for the disposition of all investigational products. The Investigator is responsible for ensuring that a current record

of product disposition is maintained, and product is dispensed only at an official study site by authorized personnel as required by applicable regulations and guidelines. Records of product disposition, as required by federal law, consist of the date received, date administered, quantity administered, and the subject number to whom the drug was administered.

The Investigational Pharmacist will be responsible for maintaining accurate records of the shipment and dispensing of the investigational product. The pharmacy records must be available for inspection by the DMID monitoring contractors, and is subject to inspection by a regulatory agency (e.g., FDA) at any time. An assigned Study Monitor will review the pharmacy records.

Unused investigational product will be stored at 25°C (77°F); excursions permitted to 15-30°C (59-86°F) [See USP Controlled Room Temperature] in the Investigational Pharmacy until monitored and released for disposition as applicable. At study completion or termination, all unused investigational product will be disposed in accordance with the MOP following complete drug accountability and monitoring. Final disposition of the unused study product will be determined by DMID and communicated to the participating sites by the DMID Clinical Project Manager.

6.5 Assessment of Subject Compliance with Study Intervention/Investigational Product

Subjects will be requested to bring study drug with them to all visits during the Treatment Phase. Remaining pill count will be done by the site staff during each visit to assess compliance. If subjects forget to bring in their study drug or they lose their container, subject interview and study diary will be used to confirm medication adherence.

6.6 Concomitant Medications/Treatments

Subjects may receive any therapy that is deemed appropriate to treat the signs and symptoms of Norovirus after randomization at the discretion of their treating provider except for nitazoxanide and oral immunoglobulin. This can include:

- Intravenous immunoglobulin
- Changes in immunosuppression
- Anti-motility agents

Any treatment utilized should be included on the concomitant medications at the time of enrollment. Any concomitant medication pre- or post-randomization that is being used to treat the signs or symptoms of Norovirus should be marked as such on the Case Report Form for the entire duration of the study. Likewise, any change to immunosuppressive therapy would have a

note in the Case Report Form noting if the change was made because of elevated drug levels, for treatment of Norovirus or for other purposes. Concomitant medications will be collected through visit 12 (Day 180 after initial dose of study treatment) or early termination, whichever occurs first. If the Investigator learns that the subject has taken a prohibited medication (see inclusion/exclusion criteria) prior to the last dose, the Investigator will contact the DMID Medical Officer and CPM for instructions regarding the subject's continuation in the study.

Medications that might interfere with the evaluation of the investigational product should not be used unless absolutely necessary.

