5.2 Subject Exclusion Criteria

Subjects meeting any of the exclusion criteria at baseline will be excluded from study participation

1. Other identified infectious causes of diarrhea at screening*.
2. Any condition that would, in opinion of the Site Investigator, place the subject at an unacceptable risk of injury or render the subject unable to meet the requirements of the protocol.
3. Subjects receiving oral or intravenous immunoglobulin therapy concurrently or in the 14 days prior to enrollment.
4. Nitazoxanide use for any illness in the previous 30 days prior to randomization.
5. Have received experimental products within 30 days prior to the study entry or plan to receive experimental products at any time during the study
6. Known sensitivity to nitazoxanide or any of the excipients comprising the nitazoxanide tablets.
7. Subjects unable to swallow oral medications.
8. Subjects with ostomy.
9. Women who are pregnant or lactating or have a positive urine pregnancy test at screening/enrollment/Day 1.

Co-enrollment in other studies is allowed if none of the above exclusion criteria are met.

*Alternative diagnosis requiring treatment would be considered a co-infection; if the testing is positive for a pathogen that the PI does not feel is causing the symptoms, they may be included but the PI or his/her designee must document that the positive test is not clinically significant, does not require treatment and is not causing the symptoms making the patient eligible for enrollment.

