Serum Immunoglobulin Testing (Serum total Ig and Norovirus-specific levels): Day 1 will assess baseline values, Day 28 will assess end of treatment levels. The proportion of subjects with ≥ 4 -fold rise in Norovirus-specific Ig titers from Day 1 will be assessed at Day 28 comparing

the nitazoxanide treatment group to the placebo group. In addition, the ratios of Norovirus-specific IgG to total IgG will also be compared between the nitazoxanide and placebo groups.

For exploratory outcome 22, an ANCOVA model will first be used to compare the treatment and placebo groups with respect to difference in changes of Norovirus-specific serum and stool IgA, IgM and IgG between Day 1 and Day 28 and between Day 1 and Day 60 (for stool only). A mixed effects model will then be used to compare the treatment and placebo groups with respect to difference in the changes of Norovirus-specific serum and stool IgA, IgM and IgG, which will use the longitudinal data observed at all three time points.

For exploratory outcomes 23-26, a Fisher's Z-transformation will be applied to the Pearson correlations between change in total lymphocyte count and T cell subsets at Day 1 and 180 and clinical resolution of symptoms in both the treatment and placebo groups, which will then be compared using a Z-test.

Pharmacokinetics and Dose Response:

For exploratory outcome 27, plasma concentrations of nitazoxanide metabolites in subjects consenting for PK blood draws at two time points will be described and summarized. Descriptive statistics (e.g. n, mean, standard deviation, % CV, median, and range) will be calculated for each sampling time.

Cox proportional hazard regression models will be used to examine the dose response relationship of Day 7 and Day 21 nitazoxanide metabolite concentrations on time from randomization until initial clinical resolution of Norovirus symptoms for at least 48 hours through Day 180. Additional analyses of PK endpoints may be described in the SAP.

Natural History of Disease:

Exploratory outcomes 28-31 are all time-to-event outcomes. They will be analyzed similarly as exploratory outcome 1.

Exploratory outcome 32 will be assessed similarly to exploratory outcome 14.

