3. STUDY OBJECTIVES AND ENDPOINTS

3.1. Study Objectives

3.1.1. Primary Objective:

- To assess the clinical efficacy of nitazoxanide for the management of acute and chronic Norovirus in transplant recipients.

3.1.2. Secondary Objectives:

- To assess the virologic efficacy of nitazoxanide.
- To assess the safety of nitazoxanide for the management of acute and chronic Norovirus in transplant recipients.

3.1.3. Exploratory Objectives:

- To assess initial clinical improvement in Norovirus Disease through 28 and 180 days.
- To assess markers of virologic improvement in Norovirus Disease through 28 and 180 days.
- To assess the contribution of immunologic response to Norovirus to the clinical course of disease in treated and untreated subjects.
- To define the pharmacokinetics and dose response relationships of nitazoxanide.
- To define the natural history of Norovirus in nitazoxanide treated and untreated subjects.

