Number of Type 6 or 7 Stools:

The number of Type 6 or 7 stools through Day 28 will be defined as the sum of the responses to the quantitative Daily Diary Diarrhea Questions during the Treatment Phase (see above). Missing responses will be left as missing.

Number of Days of IV Hydration or Total Parenteral Nutrition (TPN) Therapy:

The number of days of IV hydration or TPN therapy will be defined as the number of days with a concomitant medication with any indication related to IV hydration or TPN therapy. A blinded review of the concomitant medication data will be performed by the Medical Monitor to identify medications that should be included in the analysis. Days prior to Day 1 will not be included in the calculation of the number of days. Medications that are ongoing after Day 28 will be censored at 28 days.

Co-pathogen Status:

Co-pathogen status will be determined by the BioFire stool pathogen screen on Days 1 and 180. Co-pathogen status will be determined on Days 7, 14, 21, 28, 60, 120, and with recurrent diarrhea if unformed stool is present on study day. Analyses will only include whether pathogens were detected or not and will not differentiate by co-pathogen type. The listing will include which co-pathogens were detected at each subject/visit ([Listing 18](#)).

Secretor Status:

Saliva is collected at screening to determine H type 1 secretor status (phenotyping), while a buccal swab is collected to perform FUT2 genotyping. Phenotype and genotype results will either be “secretor” or “non-secretor” for each subject.

Norovirus-Specific Immunoglobulins (Ig):

Results below the lower limit of detection (LLOD) will be imputed as $\frac{1}{2}$ the LLOD. Results above the upper limit of detection (ULOD) will be imputed as the ULOD.

Responders:

A subject is classified as a responder if he or she has a four-fold or greater increase in Norovirus-specific Ig titers compared to baseline (Day 1).

Study Day:

Study day will be reported as the number of days from randomization with the day of randomization reported as study day 1.

Days Post-Randomization:

Days post-randomization will be reported as the number of days since randomization; if an event began on the day of randomization, the days post-randomization is reported as 0.

Duration:

Duration will be reported as the difference between the start and end dates, inclusive of the day the event started.

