10. IMMUNOGENICITY

Summary statistics including the number of subjects with a valid result, geometric mean titer and 95% CI, median, minimum, and maximum will be provided by study day and treatment group for Norovirus-specific serum and stool IgA, IgM, and IgG in [Table 37](#). In addition, geometric mean fold-rise and proportion of responders (defined as four-fold or greater increase from baseline) with 95% confidence intervals will be displayed in [Table 38](#). Confidence intervals for the proportion of responders will be Wilson score two-sided 95% CIs. [Table 37](#) and [Table 38](#) will also provide summaries for Total Serum IgG and the ratio of Norovirus-specific IgG to Total IgG for each study day and treatment group.

The change in Norovirus-specific serum and stool IgA, IgM, and IgG between Day 1 and Day 28 and Day 1 and Day 60 will be assessed using analysis of covariance (ANCOVA) adjusting for baseline assay value. The analysis will be conducted in the mITT population. [Table 39](#) will present the observed means and standard deviations of the change in Norovirus-specific serum and stool IgA, IgM, and IgG between Day 1 and Day 28 and Day 1 and Day 60 for each treatment group. Levene's test and normality checks will be carried out to check if the assumptions of ANCOVA are met. If assumptions of ANCOVA have been met, the adjusted mean, standard error, and 95% confidence intervals will also be presented for each treatment group. The p-value for the test of between treatment differences will also be presented. If the assumptions of ANCOVA are not met, transformations of the change in assay variable may be utilized to correct any skewness in residuals or heterogeneity of the variances. If a transformation of the dependent variable is used, a footnote in the table will denote which transformation was used in the analyses. If the assumptions of ANCOVA cannot be met through transformation of the dependent variable, only the observed mean, standard deviation and 95% confidence intervals of the unadjusted change in Norovirus-specific serum and stool IgA, IgM, and IgG between Day 1 and Day 28 and between Day 1 and Day 60 will be reported.

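### Intravenous immunoglobulin is allowed after randomisation, but the SAP has no rule for serum IgG samples drawn after an infusion (exploratory endpoints only)

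*Protocol*

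**What the plan says.** **Treatment.** Protocol 6.6 leaves post-randomisation therapy to the treating provider: "Subjects may receive any therapy that is deemed appropriate to treat the signs and symptoms of Norovirus after randomization". Only nitazoxanide and oral immunoglobulin are barred, and the first named example of an allowed therapy is "Intravenous immunoglobulin". SAP 4.4.7 repeats this. At entry the rule differs: Protocol 5.2 excludes "Subjects receiving oral or intravenous immunoglobulin therapy concurrently or in the 14 days prior to enrollment". Medication used for norovirus "should be marked as such on the Case Report Form for the entire duration of the study".

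**Antibody analysis.** The related exploratory objective (SAP 3.1) reads "To assess the contribution of immunologic response to Norovirus to the clinical course of disease in treated and untreated subjects". SAP 3.3 sets the responder rule: "A subject is classified as a responder if he or she has a four-fold or greater increase in Norovirus-specific Ig titers", counted from Day 1. SAP section 10 assesses "The change in Norovirus-specific serum and stool IgA, IgM, and IgG between Day 1 and Day 28", and likewise to Day 60, by ANCOVA. It adds geometric mean titres, geometric mean fold rise, responder proportions, a mixed model, and correlations with the day of resolution and the first undetectable PCR. Protocol 11.4.5 adds that "the ratios of Norovirus-specific IgG to total IgG will also be compared" between arms, and SAP Tables 37 and 38 carry that ratio.

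**Serum sampling days.** The protocol analyses serum at Days 1 and 28 and keeps Day 180 serum for future use (Table 6). The SAP (4.5.2 and section 10) adds serum at Day 60.

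**The concern.** An immunoglobulin infusion delivers the substance that the assay measures. A subject infused between randomisation and the Day 28 or Day 60 draw can show a rise in serum IgG that comes from donors. Under the SAP that rise counts as the subject's response, because nothing tells the analyst to treat the sample differently.

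Infusion is discretionary and aimed at symptoms, so its use may also differ between arms. An arm difference in fold rise, responder rate or ratio could then partly reflect who was infused. What is at stake is how the serum IgG results are read within one exploratory objective.

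**Working it through.** The plan states no figure on this point, so there is none to reproduce. The check is a search for a rule, followed by illustrations under stated assumptions.

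**1. Is there any handling rule?**

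| Place | Content | Immunoglobulin rule? |
|---|---|---|
| SAP 6.3.4, immunogenicity population | At least one dose and one stool or serum Ig result | None |
| SAP 3.3, responder | Four-fold rise from Day 1 | None |
| SAP 10, ANCOVA | Adjusts for baseline assay value | None |
| SAP 10, mixed model | Treatment, time, their interaction, subject random effects | None |
| SAP 10, correlations | IgG change against resolution day or first undetectable PCR | None |
| SAP 6.4, sensitivity subgroups | Additional nitazoxanide; chromaturia | None |
| SAP 6.5, missing data | Imputes diary data only | None |

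**2. Can the assay separate donor from host IgG?** Protocol 8.2.2 (item 4) detects bound antibody with anti-human Ig reagents, for both total IgG and norovirus-specific IgG. No described step distinguishes the source. Donor IgG therefore enters total IgG directly. It enters norovirus-specific IgG to the extent that the product contains such antibody, which the documents do not state.

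**3. Responder rate.** SAP 6.6 gives 31 enrolled. An even split (assumed) gives 31/2 = 15.5, taken as 15 per arm. One false responder adds 1/15 = 6.7 percentage points. With no true responders:

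- 1 false responder: 1/15 = 7%
- 2 false responders: 2/15 = 13%
- 3 false responders: 3/15 = 20% (Wilson 95% interval 7% to 45%)

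**4. Geometric mean fold rise.** Suppose nobody responds, and a fraction *f* of the arm has a passive rise of *F*-fold. The geometric mean fold rise is then *F*^*f* instead of 1.00.

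| | f = 10% | f = 20% | f = 30% |
|---|---|---|---|
| F = 2 | 1.07 | 1.15 | 1.23 |
| F = 4 | 1.15 | 1.32 | 1.52 |

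Both *f* and *F* are assumptions.

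**5. Ratio of specific to total IgG.** Write the subject's own values as *S* and *T*, and the donor contribution as *s* and *d*. The sample then reads (*S* + *s*)/(*T* + *d*). This lies between *S*/*T* and *s*/*d*. It moves up if the product is richer in norovirus antibody than the subject's own IgG, and down if it is poorer. The direction cannot be told from the documents.

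**6. Correlation with resolution day.** A simulation used 15 subjects, exponential resolution times with a median of 100 days capped at Day 180, and infusion in 30% or 60% of subjects unresolved after Day 14. The passive rise was 2- or 4-fold, on a background log2 change with SD 1 and no true association. It did not model infusion timing against the draw. Mean spurious correlations:

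- 2-fold rise: 0.03 (30% infused), 0.07 (60% infused)
- 4-fold rise: 0.06 (30% infused), 0.11 (60% infused)

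**The case against.** The best reply is that this is conditional and confined. No infusion frequency is given. Protocol 6.6 asks that medications which might interfere with evaluation of the product be avoided unless absolutely necessary, and Protocol 2.1 calls the evidence for systemic immunoglobulin conflicting. The endpoints are exploratory, and SAP 14.2 describes the post-closure analyses as primarily descriptive. Listing 32 already shows each medication with dates and indication, and Table 115 counts medications by therapeutic subgroup and arm. Deleting post-infusion samples could itself bias the comparison, because missingness would depend on how the subject fared after randomisation.

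Most of this stands as a limit on size. None of it is an analysis rule: discouraging a drug does not say what to do with a sample taken after it, and a listing leaves the tables unchanged. The SAP does run a sensitivity analysis without subjects who took additional nitazoxanide, so a parallel step here would fit its own approach. The point about deletion is right, and it argues against making the restricted analysis the main one.

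A reader might also note that Protocol 6.6 refers to prohibited medication by pointing to the entry criteria, which include concurrent intravenous immunoglobulin. That sits awkwardly with the list of allowed therapies, and the two statements should be reconciled. Neither reading supplies a rule for the samples.

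Three stronger readings are tempting and not supported:

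- **Placebo will show a falsely larger IgG response.** The documents do not say who will be infused or how often in each arm.
- **The correlations with resolution day are seriously confounded.** The simulated effect is small.
- **The immunologic objective fails.** It also rests on serum IgA and IgM, stool immunoglobulins, lymphocyte counts and T-cell subsets, which are not part of this point.

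**Conclusion.** The gap is real and minor. Followed as written, the plan would count donor IgG as the subject's response in any infused subject whose serum is drawn afterwards. The measures most exposed are the geometric mean titre, fold rise, four-fold responder status and the ratio.

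The scale of about 6.7 percentage points per false responder rests on roughly 15 subjects per arm. Whether any subject would cross the four-fold line passively is unknown. If no one was infused before the Day 28 or Day 60 draw, there is no bias. The primary and secondary endpoints do not depend on these samples.

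**What to change.** Add a paragraph to SAP section 10:

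- Flag every serum IgG sample collected after any post-randomisation immunoglobulin infusion. Identify infusions by drug name and date on the concomitant-medication form, whatever the indication. The norovirus-treatment mark alone would miss infusions given for another reason.
- Report infusions by arm and by timing relative to the Day 28 and Day 60 draws.
- Present the serum IgG results with and without the flagged samples: norovirus-specific IgG in Tables 37, 38, 39, 42 and 47; total IgG and the ratio in Tables 37 and 38 only. Table 46 holds lymphocyte and T-cell data and needs no change.
- State that a rise after infusion is not to be interpreted as an immune response.

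The cost is a little extra programming on data already collected, and a few values lost in the restricted version. Losing them may be informative, which is why both versions are shown. SAP 6.2 places reporting after database lock, so the rule can be fixed before results are seen if it is added before then. No treatment rule changes.
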